1.4. Dose Rationale and Risk/Benefits

The doses used in previous human studies ranged from 30 to 900 pmol/kg/min (0.006 to 0.18 mg/kg/hr) (79; 81; 86-91). Schirra et al.(79) demonstrated that

under physiological post-prandial plasma levels of GLP-1 (achieved by an intravenous infusion) administration of exendin-(9-39) at 30 and 60 pmol/kg/min (0.006 and 0.012 mg/kg/hr) significantly reduced the glucose infusion rate required to maintain blood glucose at 140 mg/dL in normal subjects, while a dose of 300 pmol/kg/min (0.06 mg/kg/hr) totally abolished the elevated demand for exogenous glucose under the experimental conditions. Furthermore, at euglycemia, infusion of exendin-(9-39) at 300 pmol/kg/min (0.06 mg/kg/hr) significantly raised basal glucose and glucagon. Edwards et al.(81) studied the effect of exendin-(9-39) on fasting plasma glucose in normal adult volunteers. They found that exendin-(9-39) infused at a dose of 500 pmol/kg/min (0.1 mg/kg/hr) increased fasting plasma glucose significantly compared with controls infused with saline. After cessation of exendin-(9-39) infusion, the plasma glucose level in response to exendin-(9-39) dropped to that of the control. In summary, these studies demonstrated that at a dose of 300 pmol/kg/min (0.06 mg/kg/hr), exendin-(9-39), abolishes the effects of physiologic post-prandial plasma levels of GLP-1, and that a higher dose of 500 pmol/kg/min (0.1 mg/kg/hr) increases fasting plasma glucose levels in normal subjects. In these studies, exendin-(9-39) was well tolerated by all subjects and there was not effect on pulse or blood pressure. No adverse effects related to exendin-(9-39) were reported in the previously discussed studies.

[figure not shown]
In our studies in mice with a null mutation of SUR-1, a pilot study demonstrated that a dose of 150 pmol/kg/min (0.03 mg/kg/hr) was effective in increasing fasting blood glucose levels, while a lower dose of 50 pmol/kg/min (0.01 mg/kg/hr) did not have an effect. In our pilot human studies, we have used a dose ranging from 100-500 pmol/kg/min (0.02-0.1 mg/kg/hr). From these studies the higher dose (500 pmol/kg/min) was given at the end of the infusion elevating blood glucose levels after a long fast (18 hrs). These doses were well tolerated. We have studied 2 neonates at this dose level administered over 6 hrs and did not find an effect on glucose infusion rates.

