3.3. Study Population

Subjects will be recruited from patients referred to the Hyperinsulinism Center at The Children's Hospital of Philadelphia, the largest center in the USA, with approximately 30 referrals/year of children with medically-unresponsive hyperinsulinism and an equal number of children with medically-responsive hyperinsulinism. Three hundred and sixty one pancreatectomies have been performed in children with congenital hyperinsulinism within the last 16 years at this center. We plan to enroll approximately 20 additional subjects, beyond the 9 subjects already enrolled up through Amendment 6, making a total number of approximately 30 subjects for about 27 evaluable subjects and to include at least some subjects with diffuse disease.

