6. Feedings: Infants will be allowed to continue feedings by mouth or by nasogastric/gastrostomy tube. Feedings will be continued every 3 hours and the volumes offered will be maintained equal during the two 9 hr study

- periods. The volume taken with each feeding will be recorded. Only intravenous glucose will be adjusted to maintain euglycemia.
7. Randomization: The investigational drug services will assign the order of the studies by randomization. They will inform the PI, study coordinator, and CTSC.
 8. Intravenous infusion of exendin-(9-39) and vehicle. All subjects will receive an infusion of exendin-(9-39) and vehicle for 9 hours on two separate days and in random order. Exendin-(9-39) /vehicle will be infused intravenously over a period of 9 hours starting at approximately the same time \pm 90 minutes on each day. The starting dose of exendin-(9-39) will be 1000 pmol/kg/min (0.2 mg/kg/hr). The dose will be escalated as outlined below. The volume of saline to be infused will be calculated to match the volume rate of exendin-(9-39).
 9. Post-infusion follow-up for subjects who have been able to discontinue dextrose infusion. Subjects who have been able to discontinue the dextrose infusion and who are not on supplemental dextrose infusion at the end of the study will continue to be monitored without additional dextrose infusion for up to 3 hours after the end of the study drug infusion, or until blood glucose is $<$ 70 mg/dL (whichever comes first). In addition to blood glucose monitoring every 30 minutes and betahydroxybutyrate every 1 hr from a capillary sample, a venous sample will be drawn at the end of 3 hours (or when blood glucose $<$ 70 mg/dL, whichever comes first) for plasma insulin and glucose.
 10. Dose schemes.

Scheme #1 (completed as of date of Protocol Amendment 7): exendin-(9-39) infused for 12 hrs at a dose of 100 pmol/kg/min (0.02 mg/kg/hr).

Scheme #2 (completed as of date of Protocol Amendment 7): exendin-(9-39) infused for 12 hrs at a dose of 200 pmol/kg/min (0.04 mg/kg/hr).

Scheme #3 (completed as of date of Protocol Amendment 7): exendin-(9-39) infused for 6 hrs at a dose of 500 pmol/kg/min (0.1 mg/kg/hr).

Scheme #4 (new as of date of Protocol Amendment 7): Dose escalation will be done as described below:

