The goal of this study is to find the intravenous dose of exendin-(9-39) (and the plasma concentration) that is necessary to completely abolish the need for exogenous glucose administration to maintain normal blood glucose in children with congenital hyperinsulinism. The sample size of three for each dosing regimen is a sample of convenience and not based on statistical considerations. However, we offer the following considerations based on our previous studies: for the first 9 subjects studied under this protocol the mean \pm standard deviation (SD) baseline glucose infusion rate (GIR) was 13.2 ± 4.8 mg/kg/min. Our hypothesis is that exendin-(9-39) will decrease the glucose infusion rate required to maintain blood glucose > 70 mg/dL. A paired test is called for to compare the two conditions – exendin-(9-39) and vehicle; however, since we do not actually know the SD of differences, our sample size calculation is based on the more conservative t-test for independent samples, and we use the SD of 4.8 as an estimate of the common SD; using a two group t-test with a 0.05 two-sided significance level.

Reduction in GIR	Sample size for 80% power	Sample size for 90% power
25%	34	45
50%	9	12
100%	3	4

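### Section 3.5 calls its independent-samples sizing more conservative than a paired calculation; that is not guaranteed at these cohort sizes, and 3 infants do not give 80% power for a 100% reduction

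*Combined protocol and SAP*

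**What the plan says.** All references are to the combined protocol and SAP.

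- Section 3.5 describes three infants per dosing regimen as a convenience sample without statistical basis, then offers power considerations. It reports that in the first nine subjects "baseline glucose infusion rate (GIR) was 13.2 ± 4.8 mg/kg/min".
- It says a paired comparison of drug and vehicle is needed, but "since we do not actually know the SD of differences, our sample size calculation is based on the more conservative t-test for independent samples". It adds that "we use the SD of 4.8 as an estimate of the common SD", "using a two group t-test with a 0.05 two-sided significance level".
- Under the column "Reduction in GIR" the table gives 34, 9 and 3 for 80% power and 45, 12 and 4 for 90% power, for reductions of 25%, 50% and 100%.
- Section 3.4 item 8 sets out the crossover: "All subjects will receive an infusion of exendin-(9-39) and vehicle". Sections 3.2 and 3.5.4 describe the same design. The dose table in section 3.4 allows cohorts of 3 to 6.
- Section 3.3 plans about 20 further subjects, "beyond the 9 subjects already enrolled up through Amendment 6". Section 3.4 lists Schemes 1 to 3 as completed. Section 1.4 says that two neonates given 500 pmol/kg/min over 6 hours were studied and that the investigators "did not find an effect on glucose infusion rates".

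**The concern.** Two things look wrong. First, the protocol already had nine infants studied under it and uses their baseline SD, yet it treats the SD of their drug-minus-vehicle differences as unknown and gives no reason. Second, an unpaired calculation is safely pessimistic in large samples whenever the two days are positively correlated. In very small samples this can fail: the paired test loses half the degrees of freedom, and at n = 3 that loss is severe.

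The table is the only quantitative power statement in the plan. A reader will take from it that three infants are enough to detect the trial's stated goal, complete removal of exogenous glucose, and that the figure errs on the safe side.

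**Working it through.** **Inputs.** From section 3.5: mean baseline GIR 13.2 and SD 4.8 mg/kg/min; two-sided alpha 0.05; power 80% and 90%. The reductions to detect are 0.25 × 13.2 = 3.3, 0.50 × 13.2 = 6.6 and 1.00 × 13.2 = 13.2 mg/kg/min. The SD of differences is not given. I assume either 4.8√(2(1 − ρ)) for within-infant correlation ρ with equal variances, or, in the target case, the vehicle-day SD.

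**1. Reproduce the table.** Unpaired t-test, noncentrality Δ/(4.8√(2/n)), df = 2n − 2, n per condition. The fractional solutions are 34.2, 9.4 and 3.4 (80%) and 45.4, 12.2 and 4.03 (90%). Rounded to the nearest integer they give all six stated values. Because they are not rounded up, the formula's own power at the stated n = 3 is 71.4%, and at the stated n = 9 it is 78.2%.

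**2. Paired power in the target case.** If GIR on drug is 0 in every infant, each difference is that infant's vehicle-day GIR, so the SD of differences is the vehicle-day SD, taken as 4.8. The paired test has noncentrality (13.2/4.8)√n = 2.75√n and df = n − 1. At n = 3 this is 2.75 × 1.732 = 4.76 against a critical value of 4.30 on 2 df. The unpaired formula has 2.75 × √1.5 = 3.37 against 2.78 on 4 df.

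| n | Paired power | Unpaired power |
|---|---|---|
| 3 | 68.6% | 71.4% |
| 4 | 94.0% | 89.7% |
| 5 | 99.3% | 96.6% |
| 6 | 99.9% | 99.0% |

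So 80% needs 4 infants, and the stated 4 for 90% holds. Simulation at n = 3 also gives 68.6%. The gap between 80% and 68.6% has two parts: 80 − 71.4 = 8.6 points from rounding down, and 71.4 − 68.6 = 2.8 points from using the unpaired formula.

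**3. When is the unpaired formula conservative?** Under equal variances and a difference of 13.2, unpaired power exceeds paired power at the same n unless ρ is above about 0.54 (n = 3), 0.39 (n = 4), 0.30 (n = 5) or 0.24 (n = 6). At ρ = 0, paired power is 45%, 73%, 89% and 96% for n = 3 to 6, against 71%, 90%, 97% and 99% unpaired.

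**4. The other rows.** Read as numbers of infants in the crossover, the stated sizes reach their paired targets once ρ is about 0.04 (34) or 0.03 (45) in the 25% row, and 0.17 (9) or 0.11 (12) in the 50% row. At ρ = 0.5 the SD of differences is 4.8√(2 × 0.5) = 4.8, and 80% power needs 19 infants rather than 34, and 7 rather than 9.

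**The case against.** The strongest reply is that nothing in the trial turns on this table. Section 3.5 says the cohort size is a convenience sample, and section 3.4 governs expansion and success by counting infants off dextrose, not by a t-test within a cohort. Section 3.5.4 plans mixed models and does not say they are fitted per cohort. This stands, and it limits the point to a stated figure and its wording.

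A reader might infer that the unpaired formula is anti-conservative throughout cohorts of 3 to 6. The documents' figures do not support that: at an SD of differences of 4.8 it is conservative at 4, 5 and 6. The correlation thresholds in step 3 also assume equal variances, which cannot hold if GIR on drug is 0 in every infant. They show that conservatism is not a property of the formula; they do not describe the target case. Most of the shortfall at n = 3 is rounding: rounded up, the unpaired formula also asks for 4.

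A reader might also infer that a usable SD of differences was in hand and ignored. That goes too far. The text does not say that all nine infants completed both days, and item 8 describes the current 9-hour regimen. Schemes 1 to 3 used 100 to 500 pmol/kg/min over 12 or 6 hours, so their variability may not carry over to the new doses. An SD from nine pairs would also be imprecise: its 95% limits run from √(8/17.53) = 0.68 to √(8/2.18) = 1.92 times the estimate. These are reasons to report it with its interval and a caveat. They do not explain why neither the SD nor a reason for its absence is given.

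**Conclusion.** The claim that the unpaired calculation is more conservative is not guaranteed, and it is weakest at the stated regimen size of three. In the target case, with a vehicle-day SD of 4.8, the 100%/80% cell is wrong: 3 infants give 68.6% paired power, or 71.4% by the plan's own formula, and 4 are needed. The 100%/90% cell holds. In the 25% and 50% rows the table is adequate at very modest correlation and overstates the need at correlation 0.5.

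This rests on normally distributed GIR, on the baseline SD of 4.8 standing in for the vehicle-day SD, and on a simple paired test without a period term. It is a correction to a non-binding power statement. It does not show that the cohorts are the wrong size.

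**What to change.** - Report the SD of exendin-minus-vehicle GIR, with its confidence interval, from the infants in Schemes 1 to 3 who completed both days, noting that their doses and infusion durations differ from the new cohorts. If it is unavailable, say why and show a range of within-infant correlations.
- Replace the table with paired power at cohort sizes 3 to 6 and at the pooled total, with any required sizes rounded up. Pooling across doses needs its own justification.
- Correct the 100%/80% cell.
- Delete the statement that the unpaired test is more conservative, or qualify it by sample size and correlation.

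The cost is one calculation and a revised paragraph. Enrolment, dosing and conduct are unchanged. The drawback is a less favourable stated figure at n = 3.

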 - a. Cohorts 1-2: at least 3 and up to 6 subjects per cohort, will be included in each of the first two cohorts. In any of the first 2 cohorts, if discontinuation of intravenous dextrose is achieved in 2 out of the 3 subjects up to three additional patients (at least 2 with diffuse disease, as defined by PET scan and/or genetics) may be enrolled in order to meet the Success Stopping Criteria (see 11a below).
 - b. Cohorts 3- 4: four subjects, with at least 2 subjects with diffuse disease. If discontinuation of intravenous dextrose is achieved in 1 or 2 of the 4 subjects, an additional subject with diffuse may be enrolled in order to meet the Success Stopping Criteria (see 11a below).

- c. The dose will be increased in $\frac{1}{2}$ log increments between cohorts as specified below:

Group	Dose Scheme (mg/kg/hr for 9 hours)	Total Dose (mg/kg)	Number of Subjects
1	0.2	1.8	3-6
2	0.6	5.4	3-6
3	2	18	3-5
4	6	54	4-6

11. Stopping Criteria:

- a. Success Stopping Criteria: the dose escalation will be stopped if in a cohort at least 2 subjects with diffuse disease are able to have dextrose infusion discontinued for the final 2 hours of the study period.
- b. Safety Stopping Criteria: if an exaggerated pharmacology effect is observed (blood glucose greater than 200 mg/dL for 2 hours off dextrose infusion) dose escalation will be stopped and the dosing algorithm will be modified to proceed with a dose that is 2 fold higher the previous level observed to be safe. Dosing will be stopped if any severe adverse event is observed.

12. Calculation of glucose infusion rate. Glucose infusion rate over the last 2 hours of the treatment period will be calculated by adding the total amount of intravenous glucose (in mg) received over 2 hours divided by the weight in Kg and by time (120 min).

13. Determination of therapeutic plasma levels, plasma half-life and pharmacokinetics of exendin-(9-39). During the infusion with exendin-(9-39) blood samples will be obtained at 1, 5, and 9 hours, and at 1 and 3 hours after the infusion ends. Should there be difficulty in establishing blood drawing lines to obtain samples of the secondary outcome variables the study will proceed with collection of the primary outcome variable only (glucose infusion rate). Plasma levels of exendin-(9-39) will be determined by mass spectrometry.

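### Sample size table, 100% reduction at 80% power: the stated formula gives about 71% power with 3 and needs 4, a minor error in one cell

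*Combined protocol and SAP*

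**What the plan says.** Section 3.5 reports a baseline glucose infusion rate (GIR) of 13.2 ± 4.8 mg/kg/min in the first nine subjects. It accepts that a paired comparison suits the design, but, "since we do not actually know the SD of differences", it sizes on two independent groups: "our sample size calculation is based on the more conservative t-test for independent samples". The remaining inputs are explicit: "we use the SD of 4.8 as an estimate of the common SD; using a two group t-test with a 0.05 two-sided significance level".

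The table then gives, for 80% and 90% power, 34 and 45 at a 25% reduction, 9 and 12 at 50%, and 3 and 4 at 100%.

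The same section limits the weight of the table. "The sample size of three for each dosing regimen is a sample of convenience and not based on statistical considerations", and the table is introduced with "However, we offer the following considerations based on our previous studies". It also states the goal: to find the dose "necessary to completely abolish the need for exogenous glucose administration to maintain normal blood glucose".

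Elsewhere, Section 3.4 item 10a sets cohorts 1-2 at "at least 3 and up to 6 subjects per cohort". Item 11a stops escalation for success when one cohort meets this condition: "at least 2 subjects with diffuse disease are able to have dextrose infusion discontinued for the final 2 hours of the study period". Section 3.5.4 compares GIR between infusions with linear mixed effects models.

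**The concern.** With only a few subjects per group, one subject more or less moves power a long way, so rounding a fractional size down matters far more in the 100% row than in the others. That row is also the one that corresponds to the stated goal, and its 3 coincides with the convenience size and with the minimum for cohorts 1-2. Someone assessing the protocol could read the table as showing that three infants give 80% power for a complete response, when the formula in the text gives less.

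The description of the two-group test as the conservative choice adds to this, because it suggests that the true position is at least as good as the printed one.

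**Working it through.** **Inputs (all from Section 3.5).** Mean GIR 13.2; common SD 4.8; two-group t-test; two-sided 0.05. Differences: 25% is 3.3, 50% is 6.6, 100% is 13.2. Assumption: the printed sizes are per group. In a crossover that equals the number of subjects.

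**Formula.** Power is the probability that a noncentral t variable with 2n − 2 degrees of freedom and noncentrality (difference/4.8) × √(n/2) exceeds the two-sided 5% critical value.

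**Reproducing the plan's table.** Solving for the fractional n that meets each target, and computing power at the printed n:

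| Reduction | Target | Exact n | Printed n | Power at printed n | n rounded up |
|---|---|---|---|---|---|
| 25% | 80% | 34.20 | 34 | 79.8% | 35 |
| 25% | 90% | 45.44 | 45 | 89.7% | 46 |
| 50% | 80% | 9.37 | 9 | 78.2% | 10 |
| 50% | 90% | 12.16 | 12 | 89.6% | 13 |
| 100% | 80% | 3.37 | 3 | **71.4%** | 4 |
| 100% | 90% | 4.03 | 4 | 89.7% | 5 |

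All six printed sizes equal the exact size rounded down (rounding to nearest gives the same result). Five cells lose at most 1.8 points. The 100%/80% cell loses 80 − 71.4 = 8.6 points.

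**The cell in detail.** The standardised difference is 13.2/4.8 = 2.75.
- n = 3: noncentrality 2.75 × √1.5 = 3.368, 4 df, critical value 2.776, power 71.4% (simulation, 400,000 runs: 71.3%).
- n = 4: noncentrality 2.75 × √2 = 3.889, 6 df, critical value 2.447, power 89.7% (simulation: 89.6%).

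**Other explanations tried.**
- Rounding of inputs: over means 13.15 to 13.25 and SDs 4.75 to 4.85, power at n = 3 is 70.3% to 72.6%. Reaching 80% would need an SD of about 4.30 or a difference of about 14.7.
- Normal approximation, n = 2 × ((1.96 + z) × 4.8/difference)²: the 100% row gives 2.08 and 2.78, which round up to 3 and 3. The table prints 3 and 4.
- One-sided t-test: 86.4% at n = 3, but the text specifies two-sided.

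**Is the two-group figure conservative in this row?** Section 3.4 item 12 defines GIR as intravenous glucose given, divided by weight and time, so it cannot be negative. A mean reduction of 100% therefore means that every subject is at zero on drug. Each subject's difference equals the vehicle value, and its SD is the vehicle SD, taken as 4.8. For a paired t-test:
- n = 3: noncentrality 2.75 × √3 = 4.763, 2 df, critical value 4.303, power 68.6%.
- n = 4: noncentrality 2.75 × 2 = 5.5, 3 df, power 94.0%.

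At n = 3 the paired test has less power than the two-group formula (68.6% against 71.4%), so the two-group figure is not conservative there. Four is the smallest size that reaches 80% under either calculation.

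**The case against.** The strongest reply is that nothing depends on the cell. The text disclaims a statistical basis for three per regimen directly before the table, escalation follows a count of subjects off dextrose, and the analysis is a within-subject mixed model. All of this stands, and it is why the point is minor. It does not make the printed figure right.

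A second reply is that the equal-SD assumption itself fails in this row. If every subject is at zero on drug, the drug-day SD is 0. Simulating a pooled two-group t-test with normal vehicle values and zeros on drug gives about 91% power at n = 3. This also stands. A reader might infer from the 71% that a cohort of three is underpowered for a complete response, or that the cohorts are too small. The documents do not support that inference: the 71% is a property of the formula as printed, and three was never justified by power.

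A third reply is precision. The SD comes from nine subjects. Assuming normality, its 95% interval is 4.8 × √(8/χ² quantile, 8 df), or 3.2 to 9.2, over which power at n = 3 runs from 95% down to 27%. An 8.6-point gap is small against that, so whole percentages are enough. The table is nevertheless stated as the result of fixed inputs, and it should agree with them.

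A reader might also infer that paired against two-group power turns on a within-subject correlation that the documents omit. In the 100% row it does not, because with GIR at zero on drug no correlation enters.

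**Conclusion.** The 100% reduction / 80% power cell is wrong as written. Under the plan's formula 3 gives about 71% power, and the smallest size reaching 80% is 4, with about 90%. The cause is rounding a required size of 3.37 down. The other five cells share the rounding but are within 2 points of target, so only this one is materially off.

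This rests on the stated mean, SD, test and significance level, on equal SDs of 4.8, and on reading the sizes as per group. The separate paired figure of about 69% rests on zero GIR in every subject on drug and on normally distributed vehicle values with SD 4.8. Neither figure is the power of the planned mixed-model analysis. The severity is minor.

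**What to change.** Change the 100%/80% cell from 3 to 4, or keep 3 and print about 71% beside it. State that the sizes are per group if that is what is meant. Rounding the other cells up (35 and 46, 10 and 13, and 5) is optional.

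If the wording on conservatism is qualified, one sentence is enough: with a 100% reduction GIR is zero in every subject on drug, so the difference has the vehicle SD of 4.8, and a paired t-test has about 69% power with 3 subjects and about 94% with 4.

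The cost is one table cell and, at most, a sentence of text. If 3 is kept, its stated power falls from 80% to about 71%. Enrolment, cohort sizes, procedures and analysis stay as they are, and three can remain a declared convenience size.
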